Fabry disease (FD) is a rare inherited lysosomal disorder caused by deficiency or dysfunction of the enzyme α -galactosidase A, which leads to an accumulation of globotriaosylceramide (Gb3) within the lysosomes of many cell types leading to cellular dysfunction and multi-organ disease¹. FD is associated with a number of characteristic clinical signs and symptoms including neuropathic pain, gastrointestinal complications, headaches, impaired sweating, vertigo, hearing impairment, angiokeratomas and cornea verticillata². Over time, FD can lead to irreversible organ damage and is a cause of premature renal failure, heart disease, cerebrovascular events and death³. As X-linked disorder, male sufferers of FD tend to be more severely affected than females⁴. Patients with FD are widely reported to have reduced health related quality of life (HRQoL) compared with the general population^{5,6} due to the debilitating symptoms and damage to vital organs. Increasing age, classical FD phenotype, more severe disease and pain have been identified as major contributors to reduced HRQoL⁶.

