9.4.1 Selection criteria for patients

Patient inclusion criteria

- Patients aged 18 years old or over at time of consent.

- Patients with a documented diagnosis of FD.
- Patients who have received ≥4 doses of ERT (with agalsidase alfa or agalsidase beta) for the treatment of FD.
- Patients who present to the participating hospital(s) or treatment centre(s) for administration of a dose of ERT (as part of their routine treatment) during the data collection period.

Patients who meet any of the following criteria will be excluded:

- Patients aged <18 years at time of consent
- Patients who are unable or unwilling to give consent for study participation.
- Patients for whom ERT preparation and administration takes place exclusively in the home setting.
- *For the time and motion evaluation:* Patients whose ERT is administered by a HCP who does not consent to be observed.

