
Summary measures of (at date of consent, unless specified):
 
 • Sex. • Age at onset of first symptoms, at FD diagnosis and at date of consent. • Duration of ERT treatment. • ERT treatment. • FD phenotype (organs involved). • FD mutation ((if known)). • Severity of FD (to be determined using the specified baseline information]). • Any other relatives (with whom the patient lives) with FD. • Number and type (agalsidase alfa / agalsidase beta) of ERT infusions received in the year prior to date of enrolment. 	
 • Sex (male / female). • Date of consent. • Age at consent. • Age at onset of first symptoms. • Date of FD diagnosis. • ERT start date. • ERT treatment under observation (agalsidase alfa / agalsidase beta). • Number of ERT infusions received in the year prior to date of enrolment, by type of treatment (agalsidase alfa, agalsidase beta). • FD phenotype (organ involvement/complications), to include any current or prior history of: hypohidrosis, neuropathic pain (and/or acroparesthesia and/or acute pain crises), cornea verticillata, angiokeratomas, hearing impairment (including deafness and/or tinnitus), cardiac events (including rhythm and/or conduction disturbances, hypertrophic cardiomyopathy or left ventricular mass index [LVMi] above normal range, myocardial infarction

	
[MI], unstable angina, congestive heart failure, major cardiac medical procedures), renal events (including reduced estimated glomerular filtration rate [eGFR], abnormal albumin creatinine ratio [ACR], proteinuria or albuminuria, dialysis, kidney transplant), central nervous system (CNS) involvement (including brain magnetic resonance imaging [MRI] changes [white matter lesions], transient ischaemic attack [TIA] or stroke), FD-related gastrointestinal [GI] symptoms, plasma lyso-Gb3 levels above normal, low white blood cells (WBC) alpha-galactosidase, other: specify)
 
• eGFR at enrolment (closest measurement prior and preferably within 12 months); date and measurement.• Urine protein levels at enrolment (closest measurement prior); date and measurement.• WBC alpha-galactosidase (closest prior to enrolment); date and measurement• LVMi at enrolment (closest measurement prior and preferably within 12 months); date and measurement.
--	---

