	
• FD mutation (name of mutation, if known, including: e.g. A143T)• Severity of FD (mild / moderate / severe), to be determined using the following baseline information:
○ Type of FD (classical / non classical). If type is unavailable, it will be inferred from the information collected below*.
▪ Number of organs involved (per medical history, as detailed above).▪ eGFR at enrolment.▪ Urine protein levels at enrolment.▪ LVMi at enrolment.▪ WBC alpha-galactosidase at enrolment.• Do any other relatives with whom the patient lives have FD (Yes / No / Not known).
	
*FD will be defined as classical if (1) multi-organ disease at baseline (≥ 2 organs) as determined by medical history or baseline values for eGFR, urine protein, LVMi, AND (2) white blood cells alpha-

	galactosidase below cut-off at baseline (≤3% wild-type).
--	---

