9.9.4 Subgroup and sensitivity analyses

The primary endpoint (and secondary endpoint, if numbers are sufficient) analyses will be conducted overall and repeated with stratification of the sample by country and by type of ERT (agalsidase alfa / agalsidase beta). If numbers are sufficient, analyses may be conducted by severity of FD (mild / moderate / severe [to be determined using the patients' baseline information, as described above]).

No sensitivity analyses are planned.

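### The fallback rule that infers classical Fabry type applies one enzyme cut-off to both sexes, so women who reach it will seldom qualify and inferred type partly encodes sex

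*Protocol*

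**What the plan says.** Protocol 9.6, Table 4, lists the baseline information used to grade severity as mild, moderate or severe. Its first item is "Type of FD (classical / non classical"). For patients whose type is not recorded the table adds: "If type is unavailable, it will be inferred from the information collected below".

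The footnote gives the inference rule. Part 1: "FD will be defined as classical if (1) multi-organ disease at baseline (≥ 2 organs) as determined by medical history" or by baseline eGFR, urine protein or LVMi. Part 2, joined to part 1 by AND: white-cell alpha-galactosidase "below cut-off at baseline (≤3% wild-type"). The footnote has no separate branch for women and no other route to a classical label.

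Both sexes can enter. The diagnostic criterion in Protocol 9.4.1 is "Patients with a documented diagnosis of FD", and Table 4 records "Sex (male / female"). Protocol 7 states: "As X-linked disorder, male sufferers of FD tend to be more severely affected than females".

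On use, Protocol 9.9.4 says: "If numbers are sufficient, analyses may be conducted by severity of FD". SAP 2.6 lists the enzyme value, the mutation and severity among the characteristics to be summarised, and adds no rule of its own for type.

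**The concern.** The enzyme condition is a gate: a patient above 3% cannot be inferred classical, whatever the organ involvement. In an X-linked disease that gate does not work alike in the two sexes. An affected man has only the mutant copy, so very low activity is a plausible marker of type in him. A heterozygous woman also has a wild-type copy, so activity at or below 3% would need nearly all the sampled cells to be using the mutant one. The argument does not depend on when the assay was taken, and applies equally to a value from before any ERT.

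If so, a man and a woman with the same organ involvement and the same mutation can receive different inferred types because of sex alone. Type is an input to severity, and severity is both a reported characteristic and a possible stratifier. Protocol 7 names classical phenotype and disease severity as major contributors to reduced HRQoL, which is a secondary outcome here, so a reader would give these labels weight. Neither document plans to show type or severity by sex, which would reveal the problem.

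**Working it through.** The plan states no figure for this rule, so there is nothing to reproduce. The check has three steps.

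**1. The rule as written.** Classical = (organs ≥ 2) AND (activity ≤ 3%).

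| Organs | 0% | 3% | 3.1% | 25% | 50% |
|---|---|---|---|---|---|
| 1 | not classical | not classical | not classical | not classical | not classical |
| 2 | classical | classical | not classical | not classical | not classical |
| 5 | classical | classical | not classical | not classical | not classical |
| 8 | classical | classical | not classical | not classical | not classical |

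Above 3% the organ count has no effect. This follows from the text alone.

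**2. How often a heterozygous woman might fall at or below 3%.** The documents give no enzyme level for women, so this step is an illustration under assumptions. Let f be the share of white cells using the wild-type copy and r the residual activity of the mutant copy. Then activity = f + (1 − f) × r, and the largest f that still meets the cut-off is (0.03 − r)/(1 − r):

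- r = 0: 3.0%
- r = 1%: 0.02/0.99 = 2.0%
- r = 2%: 0.01/0.98 = 1.0%

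Suppose f arises from n precursor clones, each using the wild-type copy with probability p. For n = 8, 16 or 32, a single wild-type clone already gives f of at least 1/32 = 3.1%. Only zero such clones will do, so P(activity ≤ 3%) = (1 − p)^n for any r up to 3%.

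| p | n = 8 | n = 16 | n = 32 |
|---|---|---|---|
| 0.5 (random) | 0.4% | 0.002% | about 0 |
| 0.3 | 5.8% | 0.33% | 0.001% |
| 0.2 | 17% | 2.8% | 0.08% |
| 0.1 (heavily skewed) | 43% | 19% | 3.4% |

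Meeting the cut-off is rare unless inactivation is strongly skewed towards the mutant copy and few clones are involved.

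**3. How many women could reach the rule.** Neither the sex split nor the share with unrecorded type is given. Assume 30-60% women, 20-50% unrecorded type, and the two independent. The base is the 120 patients expected to complete questionnaires (Protocol 9.8).

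- Low: 0.30 × 0.20 = 0.06; 0.06 × 120 = 7.2, about 7 patients
- High: 0.60 × 0.50 = 0.30; 0.30 × 120 = 36 patients

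This counts women exposed to the rule. It includes women with fewer than two organs involved and women who are truly non-classical, whom the rule labels correctly.

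**The case against.** **The premise is not in the documents.** No passage states an enzyme level for women; Protocol 7 says only that the disease is X-linked and tends to be worse in men. That is so, and the probabilities above are illustrative. Still, that a heterozygous woman has a wild-type copy follows from X-linkage, which the protocol asserts. It supports *seldom*. It does not support the stronger reading that no woman can ever be inferred classical, since heavy skewing could let some qualify.

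**The reach is small.** The rule is a fallback, the centres are specialist ones where type may usually be on record, the severity analysis is optional, and Protocol 9.9.2 and SAP 2.5 rule out comparisons between subgroups. All of this stands and keeps the point minor. Protocol 7 also expects men to be more severely affected, so some overlap of severity with sex is no error in itself. The fault is that the inference rule adds to it by construction.

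**A reader might infer that a patient with no assay is labelled non-classical by default.** The documents do not say so. Protocol 9.9.3 and SAP 2.3 restrict each analysis to patients with data available, which plausibly leaves such a type missing.

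**A reader might infer that women end up in too mild a severity group.** This cannot be shown. No algorithm maps the inputs to mild, moderate or severe, and organ count, eGFR, urine protein and LVMi may enter severity directly.

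**Conclusion.** The point holds as a defect in a fallback classification rule. As written, the rule will label most women who reach it non-classical whatever their organ involvement, so inferred type partly encodes sex. It affects type wherever that is reported and may carry into severity and its optional subgroup analysis. The primary analysis of HCP time by country and product does not use type and is unaffected.

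The conclusion rests on the text of the footnote, on X-linkage as stated in Protocol 7, and on the assumption that most women in the study are heterozygous. Its size cannot be derived from the documents. The range of 7 to 36 of 120 should not be read as a number of misclassified patients. Importance is low, but the correction is cheap.

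**What to change.** In the Table 4 footnote and in SAP 2.6:

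- Apply the enzyme-based inference to men only.
- For women without a recorded type, code type as not determinable, unless the investigators agree before analysis on a route using the mutation and organ data already collected. That route needs a mapping from mutation to type, which neither document supplies, and the mutation is recorded only where known. Not determinable is therefore the default.
- Show type and severity by sex.

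The enzyme threshold is a clinical matter, and no other value is proposed here.

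The cost is wording in two places and one extra table split, with no new data or visits. The downside is that fewer patients will have a type, so any severity subgroup will be smaller.

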9.7 Data source

Patients' demographic and clinical data will be sourced from patients' medical records and other systems within the main (specialist) participating FD centres.

For the time and motion component of the study, prospective data relating to HCP time associated with the preparation and administration of a single dose of ERT will be captured by direct observation of HCPs during the episode of care by an independent external observer or a member of the patients' care team.

Patient- and caregiver-reported outcomes will be reported directly by patients and their caregivers using anonymised-coded paper-based questionnaires. Questionnaires will be given to consenting patients and caregivers by members of the patients' whole care team during an ERT administration visit. If the ERT infusion takes place in a hospital or treatment centre, it is anticipated that the validated questionnaires (with the exception of the first work productivity questionnaire) will be completed by the patient or caregiver during the ERT infusion and returned to centre staff in sealed envelopes for forwarding to the study management company, before they leave the clinic. The first work productivity questionnaire will be completed by the patient or caregiver at home between 1 and 7 days after date of the patient's ERT infusion. The bespoke questionnaire (which requires the patient or caregiver to document the time of leaving the clinic and the time to return to home/work) will also be completed by the patient or caregiver after leaving the clinic and returned to the centre (together with the first work productivity questionnaire) at a later date, either in person (at the patient's next ERT administration attendance) or by post (using a pre-paid envelope). Alternatively, their responses to the first work productivity questionnaire, the bespoke questionnaire and the bespoke Fatigue Likert scale may be collected over the telephone during call with a member of the patient's care team, or following a reminder call from a member of the patient's care team to fill in the questionnaires. If part of the episode of care takes place in the patient's home, it is likely that all study questionnaires will be completed by the patient or caregiver at home and returned to the centre as described above.

9.8 Study size

This study aims to recruit sufficient patients to record 30 episodes per treatment per country. Given this, the number of patients recruited will range from 15 to 30 per treatment per country. To evaluate the value of the sample estimates of the population that this sample size will allow for, it will be assumed pessimistically that each patient will have one measurement; the estimates once the study is carried out will therefore have higher precision than calculated below.

The anticipated length of time for pre and post-administration activities and infusion for each treatment utilised estimates from the research of Guest et al.¹⁷ alongside clinical opinion sourced from sites in the countries of study; it was estimated that pre-administration processes would always take between 10-30 minutes, post-administration processes would take between 15-30 minutes, infusion of agalsidase alfa takes between 40 to 60 minutes and infusion of agalsidase beta would take between 90 to 180 minutes. To anticipate the precision of estimates given the sample size above, it was estimated that these times would follow a normal distribution within these ranges (as a result, the mean could be estimated by taking the middle value of the range and the standard deviation roughly approximated accordingly).

It is important to account for the fact that Fabry disease is rare and that the sample collected will represent a large proportion of the total population with disease. For instance, in the US, it was estimated that there were only approximately 7700 patients in total out of a population of about 323 million in 2016, which suggests that only 0.0024% have the disease. The estimated number of Fabry disease patients in other countries can be calculated from the prevalence of the disease in the US, by multiplying the expected proportion of the population with the disease (assuming that the prevalence is similar in the US to other countries) with the estimated total population (Brazil, Japan, Taiwan and Turkey therefore could have an estimated patient population of about 5015, 3033, 573 and 1934 patients respectively based on estimates of total population of 210 million, 127 million, 24 million and 81 million patients respectively²⁴). Accounting for this, the estimated precision of estimates of time at different sample sizes for the largest and smallest countries in the study by population can be seen in the table below.

Table 5. Sample size estimations

Cohort	Activity / Estimate	95% confidence interval at different sample sizes			
		15 patients	20 patients	25 patients	30 patients
Brazil	Pre-Admin activity Mean: 20 minutes	17m 14 - 22m 46	17m 40 - 22m 20	17m 56 - 22m 04	18m 08 - 21m 52
	Post-Admin activity Mean: 22 mins 30	20m 26 – 24m 34	20m 45 – 24m 15	20m 57 – 24m 03	21m 06 – 23m 53
	ERT Alfa Mean: 50 minutes	47m 14 – 52m 46	47m 40 – 52m 20	47m 56 – 52m 04	48m 08 – 51m 52
	ERT Beta Mean: 135 minutes	122m 33 – 147m 27	124m 29 – 145m 31	125m 44 – 144m 16	126m 37 – 143m 23
	Overall Alfa Mean: 92 mins 30	84m 54 – 100m 06	86m 05 – 98m 55	86m 50 – 98m 10	87m 23 – 97m 37
	Overall Beta Mean: 177 mins 30	160m 13 – 194m 47	162m 54 – 192m 06	164m 38 – 190m 22	165m 52 – 189m 08
Taiwan	Pre-Admin activity	17m 16 – 22m 44	17m 42 - 22m 18	17m 59 - 22m 01	18m 08 - 21m 52

	Mean: 20 minutes				
	Post-Admin activity Mean: 22 mins 30	20m 27 – 24m 33	20m 46 – 24m 14	20m 59 – 24m 01	21m 06 – 23m 54
	ERT Alfa Mean: 50 minutes	47m 16 – 52m 44	47m 42 – 52m 18	47m 59 – 52m 01	48m 08 – 51m 52
	ERT Beta Mean: 135 minutes	122m 42 – 147m 18	124m 39 – 145m 21	125m 55 – 144m 05	126m 37 – 143m 23
	Overall Alfa Mean: 92 mins 30	84m 59 – 100m 01	86m 10 – 98m 50	86m 57 – 98m 03	87m 23 – 97m 37
	Overall Beta Mean: 177 mins 30	160m 24 – 194m 36	163m 07 – 191m 53	164m 52 – 190m 08	165m 52 – 189m 08

The higher the number of patients available to sample from the more precise the estimates of time taken for each activity will be, yet even at a worse-case scenario, 95% confidence intervals should be sufficient to describe the burden associated with ERT administration. Estimates taken from countries where the sample size represents a higher proportion of the total population with the disease, such as Taiwan will also be slightly more precise.

Therefore, the target sample size for the time and motion evaluation undertaken as part of this study is 240 ERT episodes, including 60 ERT episodes (30 for agalsidase alfa and 30 for

agalsidase beta) in each participating country. Ideally, a maximum of two ERT administration episodes will initially be observed per patient (except in exceptional cases where it is determined that it is required to observe three episodes per patient due to a limited number of available patients/episodes for observation), and at least 30 patients are expected to be enrolled in each country. For countries with limited FD patient numbers, a review of episodes of care observed will be completed on an ongoing basis. It may be determined that it is possible to observe three episodes per patient in these circumstances, however only two episodes will be observed per patient wherever possible.

For the questionnaire evaluation, approximately 120 patients and 20 caregivers will be expected to fill questionnaire sets (approximately 30 patients' and 5 caregivers' questionnaire sets per country).

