2.6 Analysis of the primary objectives

Objective 1	To quantify the total time spent by HCPs in the preparation and administration of a single dose of ERT (with agalsidase alfa and agalsidase beta) in patients with FD.
Endpoint and variables required	Description of analytical approach
The total time spent by HCPs (physician / nurse / nurse assistant or healthcare assistant / pharmacist / pharmacy assistant / other) in the preparation and administration of a single dose of ERT in patients with FD	The total time spent will be treated as quantitative variables and will be summarized with mean, sd etc, as per described in section 2.5. The summary statistics will be produced separately for each country and by ERT product (agalsidase alfa or agalsidase beta).
Episode setting (hospital / infusion centre / primary healthcare centre / primary healthcare centre (preparation and set-up) with home infusion) / other (specify)	The frequency and percentages will be provided for each of these categorical variables.
ERT product administered: agalsidase alfa (Replagal®, Shire or biosimilar) or agalsidase beta (Fabrazyme®, Sanofi Genzyme or biosimilar) 
 ○ ERT dose administered. ○ Pre-medications administered 	
Secondary Endpoints Summary measures of the time spent by HCPs on the following tasks associated with the preparation and administration of a single dose of ERT (with agalsidase	The total time will be calculated by summing the difference in start and end time of these activities. This will be summarized using mean, sd, median and IQR as per section 2.5.

alfa or agalsidase beta) in patients with FD:
	

Pre-administration patient consultation:
 
 ○ Time patient arrived ○ Time patient left clinic 	
Time patient left – Time patient arrived
 
End time – Start time

Start and end time of patient consultation with HCP for pre-treatment assessment.
	
End time – start time

Start and end time of prescription writing (if additional to consultation time with patient).
	
End time – start time

Start and end time of pre-administration clinical documentation (if additional to consultation time with patient).
	

Infusion (and pre-medication) preparation activities:
	
End time – start time

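### Protocol 9.8 promises better precision than Table 5; with 30 episodes fixed per product per country this is not generally true, and the 15-patient column is a safe worst case only under the two-episode cap

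*Protocol*

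**What the plan says.** Protocol 9.8 fixes the number of episodes: "This study aims to recruit sufficient patients to record 30 episodes per treatment per country". It adds that "the number of patients recruited will range from 15 to 30 per treatment per country". For Table 5, "it will be assumed pessimistically that each patient will have one measurement", and from this the section concludes that "the estimates once the study is carried out will therefore have higher precision than calculated below". No column of the table is excepted. After the table it adds: "yet even at a worse-case scenario, 95% confidence intervals should be sufficient to describe the burden associated with ERT administration".

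On repeats, the same section says: "Ideally, a maximum of two ERT administration episodes will initially be observed per patient". For countries with few patients it leaves a way out: "It may be determined that it is possible to observe three episodes per patient in these circumstances", while keeping to two where it can.

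SAP 2.4 repeats the targets without any precision figures. For the primary endpoint, SAP 2.6 says: "The total time spent will be treated as quantitative variables and will be summarized with mean, sd etc". SAP 2.5 adds 95% confidence intervals for means where appropriate. Neither section mentions weighting by patient or correlation between one patient's episodes, so the natural reading is a plain mean over episodes. Neither document gives a within-patient correlation.

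**The concern.** Assuming one measurement per patient is cautious if the study will take extra measurements on the same number of patients. Here the number of episodes is fixed, so repeats arise only because there are fewer patients. At 30 patients there are no repeats to add precision. At 20 or 25 patients some contribute one episode and others two. A plain episode mean then gives the repeated patients double weight, which costs precision if a patient's two episodes are alike.

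Table 5 and this sentence are the only quantitative support for the study size. A reader is told to expect every printed interval to be bettered, and that even the least favourable case is adequate. Both statements need the conditions under which they hold.

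**Working it through.** **Inputs.** Ranges from Protocol 9.8: pre-administration 10-30 min, post-administration 15-30 min, alfa infusion 40-60 min, beta infusion 90-180 min. Populations: Brazil 5015, Taiwan 573. Episodes per product per country: 30. Patients: 15 to 30. The protocol says only that the SD was roughly approximated from the range; SD = range/4 is inferred because it reproduces the table. The within-patient correlation rho is not given and is taken over 0 to 1.

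**Step 1: reproduce Table 5.** Half-width = t(0.975, n-1) × SD/√n × √((N-n)/(N-1)). For Overall Beta the summed range is 115 to 240 min, so SD = 125/4 = 31.25 min.

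| Patients | Before finite-population factor | Brazil, with factor | Brazil, printed |
|---|---|---|---|
| 15 | 17m18 | 17m17 | 17m17 |
| 20 | 14m38 | 14m36 | 14m36 |
| 25 | 12m54 | 12m52 | 12m52 |
| 30 | 11m40 | 11m38 | 11m38 |

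All Brazil cells, and the Taiwan cells at 15, 20 and 25 patients, reproduce within 0.5%. The six Taiwan cells at 30 patients repeat Brazil's values to within a second and are 2.3-2.6% wider than the formula gives with N = 573 (Overall Beta: 11m38 printed, 11m22 computed).

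**Step 2: variance with repeats.** If patient i contributes k_i episodes and these sum to 30, the plain episode mean has variance

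SD² × [30 + rho × Σk_i(k_i - 1)] / 900.

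The n-patient column rests on SD²/n. The ratio of the two is n × [30 + rho × Σk_i(k_i - 1)] / 900.

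**Step 3: two-episode cap.** With n patients and 30 episodes the split is forced: 30 - n patients have two episodes and 2n - 30 have one.

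| Patients | Split | Variance ratio to matching column | Above 1 when | SE ratio at rho = 1 |
|---|---|---|---|---|
| 30 | 30×1 | 1 for any rho | never | 1.00 |
| 25 | 20×1, 5×2 | (30 + 10rho)/36 | rho > 0.60 | √(40/36) = 1.054 |
| 20 | 10×1, 10×2 | (30 + 20rho)/45 | rho > 0.75 | √(50/45) = 1.054 |
| 15 | 15×2 | (1 + rho)/2 | never | 1.00 |

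At rho = 0.8 the excess is √(38/36) - 1 = 2.7% at 25 patients and √(46/45) - 1 = 1.1% at 20. At rho = 1 the Overall Beta half-widths, before the finite-population factor, are 13m36 against 12m54 (25 patients) and 15m25 against 14m38 (20 patients). At 15 patients the standard error is 0.71 (rho = 0) to 1.00 (rho = 1) times the printed column's.

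**Step 4: bound under the cap.** Since k_i ≤ 2, Σk_i² ≤ 2 × 30 = 60. The variance is largest at rho = 1, where it equals SD² × Σk_i²/900 ≤ SD² × 60/900 = SD²/15. At rho = 0 it is SD²/30. Every two-episode split therefore lies between the bases of the 30-patient and 15-patient columns.

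**Step 5: three episodes.** Ten patients with three each: variance SD² × (1 + 2rho)/30. This exceeds SD²/15 when rho > 0.50 and reaches SD²/10 at rho = 1, a standard error √1.5 = 1.22 times that of the 15-patient column. The Overall Beta half-width is then 22m21 against 17m18, because the t multiplier also grows. Ten patients is below the stated minimum of 15. An uneven split within the stated range can do the same: 15 patients as 7×3, 1×2, 7×1 have Σk_i² = 74, pass SD²/15 when rho > 0.68, and have a standard error up to √(74 × 15/900) = 1.11 times that column's.

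**The case against.** The strongest reply is that the study-size conclusion does not rest on the disputed sentence. The least favourable printed case is the 15-patient column, and by Step 4 no two-episode split is worse. The country target of at least 30 patients for 60 episodes averages 15 patients with two episodes per product, where the sentence is true for rho below 1. The study is descriptive and sets no precision threshold that could be missed. The excess at 20 and 25 patients is small beside SDs that are themselves rough. All of this stands, and it keeps the point to the stated claim.

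Four stronger readings are tempting and should not be drawn.

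- A reader might infer that the study is materially less precise than Table 5. Under the two-episode cap the documents support at most 5.4% at either printed size, and only at high rho. Larger figures need three-episode observation, which the protocol avoids where possible.
- A reader might infer that the 30-patient column can never be bettered. Taiwan's printed values are slightly too wide. The Overall rows also add the component SDs (13.75 and 31.25 min); if components were independent, which the documents do not say, the SDs would be about 8.0 and 23.4 min. Neither supports the protocol's stated reason, which is the single measurement per patient.
- A reader might infer that SAP 2.6 must average within patient first. That never does worse than the matching column, but it is less precise than the plain mean when rho is below 0.375 (25 patients) or 0.43 (20 patients). At rho = 0 its variance is 8% larger at 25 patients (22.5/625 against 30/900) and 12.5% larger at 20 (15/400 against 30/900). It also changes the target from the mean per episode to the mean per patient.
- A reader might take this as a complaint about the standard-error method. It is not: a correct standard error would simply report the wider interval.

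**Conclusion.** The sentence in 9.8 is over-general and should be corrected. It fails at 30 patients whatever rho is, because there are no repeats. At 25 and 20 patients it is not guaranteed: it fails above rho of 0.60 and 0.75 respectively. It is right for an even two-episode split at 15 patients with rho below 1. The worst-case statement after Table 5 holds under the two-episode cap but is not assured under the three-episode exception, which the protocol itself allows.

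The 30-patient result and the bound in Step 4 need no particular rho, only that it lies between 0 and 1. The thresholds assume a common SD and correlation, exactly 30 episodes, and a plain episode mean as SAP 2.6 reads. The consequence is for how precision is described; the targets need not change on this ground.

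**What to change.** Replace the sentence in Protocol 9.8 with wording to this effect:

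> When each patient contributes one episode, the 30-patient column is the expected precision. When patients contribute repeated episodes, the precision of 30 episodes depends on the within-patient correlation. With at most two episodes per patient it lies between the 30-patient and 15-patient columns. If three episodes per patient are used, it may fall below the 15-patient column.

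Qualify the worst-case remark after Table 5 in the same way, and correct Taiwan's 30-patient column when the table is next edited.

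No change to SAP 2.6 is required on this ground; averaging by patient is an estimand and efficiency choice. The only cost is a slightly less favourable stated precision.
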